10.7. Appendix 7: Contraceptive and Barrier Guidance

10.7.1. Definitions

Participants in the following categories are considered participants who can become pregnant:

1. Following menarche
2. From the time of menarche until becoming postmenopausal unless permanently sterile (see below)
 - A postmenopausal state is defined as no menses for 12 months without an alternative medical cause.
 - A high follicle stimulating hormone (FSH) level in the postmenopausal range may be used to confirm a postmenopausal state in participants not using hormonal contraception or hormonal replacement therapy (HRT). However, in the absence of 12 months of amenorrhea, confirmation with more than one FSH measurement is required.
 - Participants on HRT and whose menopausal status is in doubt will be required to use one of the non-estrogen hormonal highly effective contraception methods if they wish to continue their HRT during the study. Otherwise, they must discontinue HRT to allow confirmation of postmenopausal status before study enrollment.
 - Permanent sterilization methods (for the purpose of this study) include:
 - Documented hysterectomy.
 - Documented bilateral salpingectomy.
 - Documented bilateral oophorectomy.
 - For individuals with permanent infertility due to an alternate medical cause other than the above, (eg, Mullerian agenesis, androgen insensitivity, gonadal dysgenesis), Investigator discretion should be applied to determining study entry.

Note: Documentation can come from the site personnel's review of the participant's medical records, medical examination, or medical history interview.

- If fertility is unclear (eg, amenorrhea in adolescents or athletes) and a menstrual cycle cannot be confirmed before first dose of study intervention, additional evaluation should be considered.

10.7.2. Contraception Guidance

| CONTRACEPTIVES ^a ALLOWED DURING THE STUDY INCLUDE: |
|---|
| 
Highly Effective Methods^b That Have Low User Dependency Failure rate of <1% per year when used consistently and correctly.
 
• Implantable progestogen-only hormone contraception associated with inhibition of ovulation^c.• IUD.• Intrauterine hormone-releasing system (IUS)^c.• Bilateral tubal occlusion.• Azoospermic partner (vasectomized or due to a medical cause) Azoospermia is a highly effective contraceptive method provided that the partner is the sole sexual partner of the participant who can become pregnant, and the absence of sperm has been confirmed. If not, an additional highly effective method of contraception should be used. Spermatogenesis cycle is approximately 90 days. 
Note: documentation of azoospermia can come from the site personnel's review of the participant's medical records, medical examination, or medical history interview.
 |
| 
Highly Effective Methods^b That Are User Dependent Failure rate of <1% per year when used consistently and correctly.
 
Combined (estrogen- and progestogen-containing) hormonal contraception associated with inhibition of ovulation^c
 
1. oral2. intravaginal3. transdermal4. injectable 
Progestogen-only hormone contraception associated with inhibition of ovulation^c
 
5. oral6. injectable |
| 
Sexual abstinence
 
Sexual abstinence is considered a highly effective method only if defined as refraining from heterosexual intercourse during the entire period of risk associated with the study intervention. The reliability of sexual abstinence needs to be evaluated in relation to the duration of the study and the preferred and usual lifestyle of the participant
 |
| 
a) Contraceptive use should be consistent with local regulations regarding the use of contraceptive methods for those participating in clinical studies.
 
b) Failure rate of <1% per year when used consistently and correctly. Typical use failure rates differ from those when used consistently and correctly.
 
c) If hormonal contraception is used, one additional barrier method must also be used during sexual activity, such as a diaphragm or diaphragm with spermicide (preferred), or male condom or male condom with spermicide (preferred), from Day 1/Randomization until 30 days after the last dose of study intervention. Hormonal implants do not require an additional barrier method to be used. If locally required, in accordance with Clinical Trial Facilitation Group (CTFG) guidelines, acceptable contraceptive methods are limited to those which inhibit ovulation as the primary mode of action.
 
Note: Periodic abstinence (calendar, symptothermal, post-ovulation methods), withdrawal (coitus interruptus), spermicides only, and lactational amenorrhea method (LAM) are not acceptable methods of contraception. Male condom and female condom should not be used together (due to risk of failure with friction).
 |

10.8. Appendix 8: Recommendations for Management of Hyperkalemia

Serum potassium checks should be completed at each visit for clinical evidence of electrolyte imbalance. If a patient has a serum potassium value of >5.5 mEq/L (5.5 mmol/L) at any time during the study, the following steps are recommended:

1. If the serum potassium value is ≥ 6.5 mmol/L, emergency management should be implemented based on the site policies and Investigator's decision.
2. If the serum potassium value is >5.5 and <6.5 mmol/L, rule out measurement errors or likely reasons for the increase (eg, sample hemolysis, metabolic acidosis, discontinuation of diuretic by the patient/lack of compliance, diet transgression).
 - a. If the causes listed above are ruled out and the patient is not receiving a diuretic, it is recommended to start a diuretic (if the patient's volume status and BP permit). The choice of a thiazide or a loop diuretic is at the discretion of the Investigator. Assess the patient's tolerability and measure their BP, eGFR, sodium, and potassium within 1 week after starting the diuretic.
 - b. If the causes listed above are ruled out and the patient is already receiving a diuretic, increase the dose of the diuretic by 50% (if the patient's volume status and BP permit). Assess the patient's tolerability and measure their BP, eGFR, sodium, and potassium within 1 week after increasing the dose. Consider correction of metabolic acidosis, if relevant.
3. In both scenario 2a and 2b, adjust the dose of diuretic accordingly after 1 week. If the patient's serum potassium value is still >5.5 mEq/L (5.5 mmol/L), reinforce diet counseling/restrictions, rule out other potential causes of hyperkalemia, and consider increasing the diuretic dose. If, after an additional week, the serum potassium value is still >5.5 mEq/L (5.5 mmol/L), reduce the dose of study intervention by 50%. For long-term prevention of hyperkalemia, consider treatment with patiromer or sodium zirconium cyclosilicate.
4. If hyperkalemia persists or recurs, study intervention must be discontinued permanently.

10.9. Appendix 9: Liver Safety: Suggested Actions and Follow-up Assessments and Study Intervention Rechallenge Guidelines

Abnormal liver function test results that meet at least one of the following criteria below will be considered AEOIs and must be reported to the Sponsor's Medical Monitor within 24 hours of awareness:

- The abnormality represents a new elevation in ALT or AST >3 times ULN, with or without an elevation of total serum bilirubin >2 times ULN.
- The abnormality represents a 2-fold increase in ALT or AST above the baseline value for the study period (ie, Day 1) in participants who had elevated values prior to starting study intervention.

In such instances, the following steps should be taken:

1. Temporarily discontinue study intervention.
2. Perform repeat testing of ALT, AST, liver specific alkaline phosphatase (ALP), and total bilirubin within 48 to 72 hours to confirm the abnormalities.
3. If the abnormality is confirmed by repeat results, the following should be done:
 - a. Complete an AEOI Report Form that documents both the liver function test findings and any associated signs or symptoms, and report by email to the SAE contact on the SAE Contact Information page ([Section 10.1.1](#)) of this protocol.
 - b. Monitor liver enzymes and serum bilirubin 2 or 3 times weekly. The frequency of retesting can decrease to once weekly or less if the abnormalities stabilize and the participant is asymptomatic.
 - c. Perform additional testing to evaluate liver function, as appropriate (eg, INR and direct bilirubin).
4. Do not resume study intervention until monitoring indicates abnormalities have resolved or stabilized.

Participants are not allowed to resume study intervention if they have the following:

- ALT or AST >8 times ULN.
- ALT or AST >5 times ULN for more than 2 weeks.
- ALT or AST >3 times ULN and total bilirubin >2 times ULN or INR of >1.5 .
- ALT or AST >3 times ULN, with symptoms of fatigue, nausea, vomiting, right upper quadrant pain or tenderness, fever, rash, and/or eosinophilia ($>5\%$ eosinophils).

Management of such participants should be closely coordinated with the Sponsor's Medical Monitor. In addition to monitoring liver function tests, the Investigator should perform other relevant clinical and laboratory measurements to identify potential causes of the abnormalities (eg, acute viral hepatitis types A, B, C, D, and E; autoimmune or alcoholic hepatitis; nonalcoholic steatohepatitis; biliary tract disease or exposure to hepatotoxic medications or environmental chemical agents). Additionally, participants who demonstrate elevated liver enzymes a second time after re introduction of the study intervention may continue in the clinical study; however, they will not receive study intervention for the remainder of the trial.

Cases of increased liver function tests will always be considered serious (ie, medically important) if they meet both the following criteria:

- Study intervention is suspected to have caused hepatocellular injury, generally shown by a confirmed elevation of 3-fold or greater above ULN in ALT or AST.
- The ALT or AST elevations are accompanied by a total bilirubin >2 times the ULN or INR of >1.5 without initial findings of cholestasis (elevated serum liver specific ALP).

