Brief Summary: This is a 28-week, open-label, multicenter, single-group Phase 2 exploratory study to determine the safety and effect of sparsentan in participants with IgAN who are at risk of disease progression to KF despite being on both stable RAASi and SGLT2 inhibitor treatment for at least 12 weeks prior to study entry.

Health Measurement/Outcome: The purpose of this study is to evaluate safety and effect of sparsentan in combination with SGLT2 inhibitors in adult participants with IgAN.

Study Intervention and Intervention Form: Sparsentan tablets

Condition/Disease: IgAN

Study Duration: The duration of the study for a participant will be up to 34 weeks.

Treatment Duration: The study design included a screening period of up to 6 weeks, treatment period of 24 weeks, and a follow-up period of 4 weeks.

Visit Frequency: Site visits will be conducted for screening, at Day 1 (baseline), and at weeks 2, 4, 12, and 24 following Day 1. Following the 24-week treatment period, study intervention will be discontinued for 4 weeks. At this time, the Investigator should resume standard of care treatment, including RAAS inhibitor treatment. Participants will return to the site for a visit at Week 28 for the safety follow-up visit.

Number of Participants:

Approximately 60 participants aged ≥ 18 years will be enrolled into this study.

Note: Enrolled means participants', or their legally acceptable representatives', agreement to participate in a clinical study following completion of the informed consent. Potential participants who are screened for the purpose of determining eligibility for the study, but do not participate in the study, are not considered enrolled, unless otherwise specified by the protocol.

Study Arms and Duration:

This study includes 3 periods: a screening period (up to 42 days), a treatment period (24 weeks) and a follow-up period (4 weeks).

All participants will be on stable doses of standard of care ACEI and/or ARB and an SGLT2 inhibitor at study entry, with prohibited concomitant medications discontinued before the baseline (Day 1) visit. The full daily dose of study intervention (sparsentan) is preferred to be taken prior to the morning meal, with the exception of the day of a study visit. Allowed doses of sparsentan during the treatment period are 200 mg and 400 mg. The goal is to titrate from the initial dose of 200 mg (Day 1) to the target dose of 400 mg at Week 2.

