Other Exclusion Criteria

14. The participant is pregnant, plans to become pregnant during the course of the study, or is breastfeeding.
15. The participant, in the opinion of the Investigator, is unable to adhere to the requirements of the study, including the ability to swallow the study intervention capsules whole.

Participants with a medical condition or abnormal clinically significant laboratory screening value not listed above that may interfere with the evaluation of sparsentan efficacy or safety will be reviewed with the Medical Monitor before consideration of the participant for enrollment. If, in the Investigator's opinion, a laboratory value at screening is deemed unlikely to be representative of the participant's true status, the Investigator may have 1 additional measurement on that variable through the Central Laboratory to assess participant eligibility. Participants who fail screening may be rescreened according to [Section 5.4](#).

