6.1. Study Intervention(s) Administered

The study intervention to be used in this study is outlined in Table 2.

Table 2: Study Intervention(s) Administered

| | |
|---|--|
| Intervention Label | Sparsentan |
| Intervention Name | Sparsentan |
| Intervention Description | Week 1: Starting dose will be 1 tablet (1 x 200 mg) taken prior to the morning meal. Starting Week 3: Dose will be titrated to 1 tablet (1 x 400 mg) taken prior to the morning meal, if tolerated and determined safe by the Investigator. |
| Type | Drug |
| Dose Formulation | Tablet |
| Unit Dose Strength(s) | 200 mg or 400 mg |
| Dosage Level(s) | Week 1: Starting dose will be 1 tablet (1 x 200 mg) taken prior to the morning meal. Starting Week 3: Dose will be titrated to 1 tablet (1 x 400 mg) taken prior to the morning meal, if tolerated and determined safe by the Investigator. |
| Route of Administration | Oral |
| Use | Experimental |
| Investigational Medicinal Product (IMP)/Non-Investigational Medicinal Product (NIMP) | IMP |
| Sourcing | Provided centrally by the Sponsor. |
| Packaging and Labeling | Study intervention will be provided in container. Each container will be labeled as required per country requirement. Additional details about packaging and labeling can be found in the Pharmacy Manual. |

Definition of IMP and NIMP is based on guidance issued by the European Commission. Regional and/or Country differences of the definition of IMP/NIMP may exist. In these circumstances, local legislation is followed.

Table 3: Study Arm

| | |
|------------------------|--|
| Arm Title | Sparsentan |
| Arm Type | Experimental |
| Arm Description | At Week 1, the starting dose will be 1 tablet (1 x 200 mg) for all participants. At Week 3, the sparsentan dose will be titrated to 1 tablet (1 x 400 mg), if tolerated and determined safe by the Investigator. |

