6.6. Dose Modification

The Investigator may titrate up the participant's dose to the target dose based on BP and lack of AEs at Week 2. Participants who tolerate the initial dose after 2 weeks but display asymptomatic systolic BP values \leq 100 mmHg, or diastolic BP values \leq 60 mmHg will continue the initial dose after the Week 2 visit without titrating up to the target dose. Participants who do not titrate up to the target dose at Week 2 for any reason, may titrate up to target dose at any time thereafter based on evaluation of the Investigator and if allowed by BP and lack of AEs in consultation with the Medical Monitor as needed. Participants who do not tolerate the initial dose for any reason at the Week 2 visit may discontinue study intervention.

Throughout the study, participants will be maintained on the maximum allowed dose of study intervention they can tolerate while secondarily maintaining BP as close as possible to the target of 125/75 mmHg. To maintain BP, the Investigator will be encouraged to either treat participants with additional anti-hypertensive agents [with the exception of ACEIs, aliskiren, ARBs, or ERAs (see [Section 10.6](#))] or withdraw anti-hypertensive agents. In the case of intolerable hypotension, withdrawal of additional anti-hypertensive agents should be accomplished before considering withdrawal or dose reduction of study intervention.

Doses may be modified (titrate up or down) at any time throughout the study for safety or tolerability reasons at the Investigator's discretion, and if appropriate, additional safety testing may be performed.

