7.1. Discontinuation of Study Intervention

During the course of the study, it may be necessary for a participant to permanently discontinue study intervention prematurely. If study intervention is permanently discontinued prematurely, the participants should return to the site for a visit as close as possible to the participant's last dose of study intervention. This visit may be a regularly scheduled visit or an unscheduled visit, and all assessments for this visit are to be completed per the regular scheduled visit or the Week 24 visit/EOT for an unscheduled visit, respectively, as listed in the SoA ([Section 1.3](#)). At this visit, the primary reason for premature discontinuation from study intervention, will be recorded on the EOT eCRF. Following this visit, participants are to complete the safety

follow-up visit as listed in the SoA ([Section 1.3](#)) within approximately 4 weeks after the last dose of study intervention.

The discontinuation of the SGLT2 inhibitor at any point during the study is not a reason for participant removal from protocol-required investigational product(s) or procedural assessments.

Reasons for removal from protocol-required investigational product(s) or procedural assessments include any of the following:

- Decision by Sponsor.
- Lost to follow-up.
- Death.
- Ineligibility determined.
- Protocol deviation.
- Noncompliance.
- Adverse event.
- Participant request.
- Pregnancy.
- Receipt of a kidney transplant or initiation of chronic dialysis.
- Diagnosis of NYHA Class II-IV CHF.
- Hyperkalemia that is resistant to treatment (see [Section 10.8](#)).

The need for additional intervention for the treatment of IgAN or the occurrence of safety endpoints are not, by themselves, criteria for discontinuation of study intervention.

The primary reason for discontinuation of study intervention, will be recorded on the EOT eCRF. Subsequent study visit data will be recorded on the visit specific eCRF (either a regular scheduled visit or unscheduled visit). Once the EOT eCRF is completed, study intervention cannot be resumed.

Additional details regarding temporary interruption or permanent discontinuation of the study intervention are outlined in [Section 7.1.2](#) and [Section 7.2](#).

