## **4.2. Definition of Study Medication**

Study interventions are all pre-specified, investigational, and non-investigational medicinal products, medical devices, and other interventions (eg, surgical, and behavioral) intended to be administered to the study participants during the study conduct.

At the Week 1 the starting dose will be 1 tablet ( $1 \times 200$  mg) taken prior to the morning meal.

Starting at week 3 the dose will be titrated to 1 tablet ( $1 \times 400$  mg) taken prior to the morning meal, if tolerated and determined safe by the Investigator.

Patients can continue initial dose without titration or have dose reductions back to the initial dose (reduced dose) after dose titration based on tolerability as described in the protocol.

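### At 200 mg, the 50% dose reduction in the hyperkalemia steps gives 100 mg, which is neither an allowed dose nor a supplied tablet strength

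*Protocol*

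**What the plan says.** **Hyperkalemia steps.** Protocol Section 10.8 sets out recommended steps for potassium above 5.5 mmol/L. Values of 6.5 mmol/L or more go to emergency management. Between those limits, the site rules out spurious or obvious causes, then starts or increases a diuretic and rechecks within a week. If potassium is still above 5.5 mmol/L, diet and other causes are reviewed and a further diuretic increase is considered. If it is still high after one more week, the site is to "reduce the dose of study intervention by 50" percent. No starting dose is mentioned. Step 4 then requires permanent discontinuation if hyperkalemia persists or comes back.

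**Doses.** The synopsis states: "Allowed doses of sparsentan during the treatment period are 200 mg and 400 mg". Table 2 in Protocol Section 6.1 gives the unit strengths as "200 mg or 400 mg" and describes the first level as follows: "Starting dose will be 1 tablet (1 x 200 mg) taken prior to the morning meal". The second level is likewise one tablet, of 400 mg.

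**Who can be on 200 mg.** Everyone starts there. Under Protocol Section 6.6, participants with asymptomatic systolic pressure of 100 mmHg or less, or diastolic of 60 mmHg or less, "will continue the initial dose after the Week 2 visit without titrating up to the target dose". The section also foresees that others will not go up, for any reason. SAP Section 4.2 adds that participants can "have dose reductions back to the initial dose (reduced dose) after dose titration".

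**The concern.** A halving rule works only if half of every permitted dose is itself a permitted dose that can be dispensed. Here that holds for one of the two levels.

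Hyperkalemia is a listed risk of sparsentan in Table 1, so a site may well need this step. The protocol also makes it plausible that the participant in question will be on 200 mg. Section 6.6 makes up-titration depend on blood pressure and the absence of adverse events, so early hyperkalemia recorded as an adverse event can itself keep someone at 200 mg. Participants held there for low blood pressure may also be those in whom the diuretic steps, which depend on blood pressure and volume status, are hard to use.

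Sites that reach step 3 at 200 mg may then act differently from one another. That is first a safety-conduct matter. It also feeds into the SAP Section 9.2 summaries of time on reduced and target dose, the counts of dose reductions, and the counts of discontinuations.

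**Working it through.** The plan states no figure on this point to reproduce. The check is dose arithmetic followed by a reading of the timing.

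**1. Halve each permitted dose**

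| Current daily dose | × 0.5 | Allowed in the synopsis? | Strength in Table 2? |
|---|---|---|---|
| 400 mg | 200 mg | yes | yes |
| 200 mg | 100 mg | no | no |

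**2. Look for a lower level elsewhere.** Protocol Section 6.6 lets the investigator titrate up or down for safety or tolerability but names no level below 200 mg. SAP Section 4.2 recognizes one reduction only, from the target dose back to the initial dose. No section mentions split tablets or alternate-day dosing; dosing is described as daily.

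**3. Work out when step 3 is reached.** About one week to the first recheck plus one further week gives about two weeks after the first high value.
- First scheduled on-treatment chemistry is at Week 2 (Schedule of Activities), so step 3 falls at about Week 4.
- A high value on Day 1 would reach it at about Day 15 (1 + 14).

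The two weeks that everyone spends on 200 mg are therefore largely over before step 3 can apply.

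**4. Define the affected group.** It consists of participants who are still on 200 mg, or have been returned to it for another reason, and whose potassium stays above 5.5 mmol/L through both rounds of management. A participant brought from 400 mg to 200 mg by step 3 itself goes next to step 4, not to a second halving.

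**5. Size, by assumption only.** The documents give neither the share remaining on 200 mg nor the rate of persistent hyperkalemia. For illustration:
- If 10% to 30% of 60 are on 200 mg: 60 × 0.10 = 6 to 60 × 0.30 = 18.
- If 5% of those have persistent hyperkalemia: 6 × 0.05 = 0.3 to 18 × 0.05 = 0.9 participants.
- If 10% do: 0.6 to 1.8 participants.

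**The case against.** The best answer is that the appendix is guidance and that sites have other documented actions. This largely stands. Section 10.8 introduces its steps as recommended. Table 1 says sparsentan can be held or discontinued for clinically significant hyperkalemia. Section 7.1.2 provides for temporary interruption, and Section 7.1 lists adverse events and treatment-resistant hyperkalemia as reasons for removal. Section 8.4.4 requires the sponsor to be notified when significant laboratory values do not recover in reasonable time. A reader might infer that a site would have no permitted course, or would decide alone; the documents do not support either. What these passages do not do is make step 3 itself workable at 200 mg, or tell the site to pass over it.

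The Pharmacy Manual, to which Section 6.2.1 refers for administration, was not available and might address splitting. Even so, 100 mg would conflict with the doses allowed in the synopsis.

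Two further inferences are tempting and should not be drawn:
- **That splitting is barred.** Exclusion 15 refers to candidates' ability to adhere, "including the ability to swallow the study intervention capsules whole". It is an eligibility criterion, not a dosing instruction, and it names capsules although the product is a tablet.
- **That the discontinuation rules flatly contradict each other.** The Section 7.1 entry, "Hyperkalemia that is resistant to treatment", refers the reader to Section 10.8, and the same list includes adverse events. A permissive risk table and a mandatory last step can both stand. What is left is a wording difference: step 4 also covers recurrence, which is wider than resistance to treatment.

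**Conclusion.** The contradiction is real and confined to 200 mg: step 3 works at 400 mg and cannot be followed at the other permitted level. This is more than missing detail, because a stated safety step conflicts with the protocol's own list of doses and strengths.

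Its reach is narrow. A reader might infer that all participants are exposed in the first two weeks; the roughly two-week delay built into the steps rules that out. Nor is the number on 200 mg the number affected, since persistent hyperkalemia is also needed. On the illustrative assumptions above, about two participants at most would meet the problem, and possibly none. The study is single-arm and descriptive with no efficacy hypothesis, and nothing here shows a material effect on the primary endpoint.

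The conclusion rests on the protocol and SAP as they stand, without the Pharmacy Manual, and takes no position on which dose or clinical rule is right.

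**What to change.** - Reconcile step 3 of Protocol Section 10.8 with the allowed doses in the synopsis, the strengths in Table 2 and the dose-modification text in Section 6.6, so that the step can be carried out at both permitted dose levels. The choice of rule belongs to the sponsor's clinical team.
- Keep the meaning of reduced dose in SAP Sections 4.2 and 9.2 consistent with the result.
- As a minor point, align the trigger in step 4, which includes recurrence, with the treatment-resistance wording in Protocol Section 7.1.

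The cost is a wording amendment to the protocol and a matching check of the SAP, with no added visits or participants. Whether supplies are affected depends on the rule that the sponsor chooses.
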